Official Title: Effects of a Rheumatoid Arthritis Self-management program-a Randomized Controlled Trial

NCT number: NCT03470740

Date of the document: 20160801

Background

Rheumatoid arthritis (RA) is a persistent systemic disease (Flurey et al., 2014; WHO, 2003). The prevalence of RA is 0.3% - 1% worldwide (WHO, 2003), and 0.6% in Taiwan (Chou, 2003). Within a decade of its onset, RA leads to work disability defined as a total cessation of employment in between 51% and 59% of patients (WHO, 2003). In Taiwan, the Ministry of Health and Welfare (2014) emphasized that people suffer from knee joint degeneration is up to 15% prevalence, and the most common cause including RA. WHO (2003) commented that although the mortality rate of RA is low, a decreased life expectancy is associated with some musculoskeletal disorders, inflammation of the multi-system, and ischemic heart disease. The impact of RA including reduction of patients' daily activities, effects on the different dimensions of the quality of life, reduce work capacity (Lee et al., 2010; WHO, 2003), and significant increase health care costs (Furner et al., 2011). Epidemiological data indicate that individuals with RA are most often diagnosed in their 40s (Lin et al., 2004). With the disease continuing into old age, we can anticipate that the number of older patients with RA is increasing on a worldwide basis. In Taiwan, the life expectancy is increase and the average life span achieves 79.84-year (Ministry of the Interior, 2015), and indicate that individuals with RA need to live with the disease for more than 40 years.

Patients' involvement in the management of their care is referred to as self-management, which has been defined by Barlow and colleagues (2002, p.178) as "the individual's ability to manage the symptoms, treatment, physical and psychosocial consequences and life style changes inherent in living with a chronic condition". Barlow further states that for SM to be effective, it needs to encompass the ability to monitor one's condition and to affect the behavioral and emotional responses necessary to maintain a satisfactory quality of life. This definition implies that SM is more than simple adherence to treatment guidelines because it incorporates the psychological and social management of living with a chronic illness. SM involves, on the patient's part, acquiring the knowledge, practicing the skills and developing the confidence to deal with disease-related problems, and making and maintaining behavioral changes to maximize well-being (Dures & Hewlett, 2012). Chronic diseases such as RA and related conditions have no 'cure', the goal of intervention is to minimize disease impact and optimize physical, emotional, and social health (Keysor et al., 2001). Day-to-day SM is extremely important in achieving optimal health outcomes, and people with arthritis use a variety of strategies to relieve symptoms or manage disease consequences (Keysor et al., 2001). Hence, SM in arthritis tends to adopt a more holistic approach including management of psychosocial consequences and life style changes (Barlow et al., 2002).

Methods

Research Design

An **experimental design** was used to examine the effectiveness of a SM intervention for RA patients.

Sample and Setting

A medical center in northern Taiwan was selected as the research setting to ensure sufficient numbers of RA patients are able to be recruited for this study, and the teaching hospital is constantly striving to improve their services, and is readily accessible to the researcher. Patients who visited the rheumatology departments of the medical center was eligible for the study and the inclusion criteria include: (1) diagnosed with RA, (2) age of 20 years or over, (3) disease considered by the treating rheumatologist to have been stable for at least 3 months, and (4) able to understand and comply with the study treatment. Patients were excluded if they are suffering from other terminal illnesses, severe dementia or another debilitating psychiatric disorder, living in a long-term care facility, and participation in another research protocol. All patients were under the medical care of their rheumatologist during the study.

Sampling Procedure

Patients were approached for recruitment when they visit in the medical center rheumatology departments. If the patients meet the inclusion criteria and agree to participate in the study then randomly assigned to the experimental and control groups were proceeded using a computerized allocation procedure in SPSS 17.0 for Windows by an independent researcher. A numbered envelope was given. The big and opaque envelopes were numbered from 1 to 260 and contained the baseline data collection questionnaires and another sealed of small opaque envelope. The small opaque envelope contained a randomly determined using the computer-generated sequence of random numbers: number zero is for the control group and number one is for the experimental group. The researcher opened the big envelop and collect the baseline data, and then open the small sealed envelope to randomly assign participants to two groups. If the patient is random assigned to the control group, the usual care of the RA was received. Another experimental group received the program. For this sampling procedure, neither the researcher nor the participant is aware of treatment group assignment until after the baseline questionnaire has been collected. The CONSORT (Consolidated Standards of Reporting Trials) flow diagram (Moher et al., 2001) will be followed to manage the random allocation.

Intervention Program

The intervention program was based on self-efficacy theory (Bandura, 1977, 1986, 2004), and the four resources of self-efficacy such as mastery experience, social modeling, social persuasion, and physical and emotional states will be incorporate to emphasize patients' knowledge, skill, and responsibility in managing their RA situations. Various sources of information affect efficacy judgments and influence how people weigh and integrate them into actions.

Instruments and Outcome Measurements

Many of the standard measuring instruments selected have been used in previous studies of people with arthritis, and have established reliability and validity. Outcome data were collected at the baseline, and 2, 3, and 6 months including RA disease activity (DAS-28), arthritis self-efficacy (ASE), physical functioning (MHAQ), quality of life (SF-36), self-management behaviors, and health care utilization.

Procedure and Data Collection

The researcher contacted the RA patients if they meet the inclusion criteria, and a face-to-face interview started. The researcher explained the purpose and procedure of the project, as well as the participants' rights and the benefits of participating. Next, participants agreeing to participate signed consent forms. Regarding collection the data, the baseline data was collected including background information, disease activity, arthritis self-efficacy, quality of life, physical functioning, self-management behaviors, and health care utilization. It followed questionnaire guide to collect data, and the person who collected the data and the researcher who visit the patient for the intervention was never the same. After completion of baseline data, patients were randomly allocated to the intervention or control group by an independent researcher. Control patients received usual care, and the intervention group received the 6-week RA self-management program. All participants were followed up for 6 months, and the data were all collected at the RA OPD when patients were back to the clinic.

Data Analysis

Data were double entered for verification and the level of significance was set at alpha of .05 using SPSS Version 17.0. ***Descriptive statistical analyses*** were used to establish baseline characteristics of RA patients using means, ranges, standard deviations, frequencies, and percentages. Background characteristics and outcomes at baseline were compared between two groups by means of chi-square tests and t-tests for independent samples. To evaluate the effect of the intervention over the total follow-up period, we used the multiple linear regression method used in the ***GEE*** (Liang & Zeger, 1986) to take into account of internal dependencies within subjects (due to the repeated measurements) and to adjust for the effects of certain factors. Effects evaluated included the main effects of time and group and two-way interaction effect(s) of time by group. A significant interaction effect of time by group would indicate a significant change from baseline to a specific later time point between the two groups. Significant interaction effect(s) in GEE results would provide evidence of intervention effects.

Ethical Considerations

The study was reviewed and approved by the Institutional Review Boards of the hospitals of the PI prior to data collection. The participants were informed both orally and in writing about the purpose of the study, assured that participation was voluntary, and the benefits of participating. To ensure the security of the intervention, the researcher discussed with the physician about the potential participants' condition and their self-management. They signed the informed consent, was guaranteed confidentiality, and was assured an anonymous presentation of the findings.

References

Albanoa, M. G., Giraudet-Le Quintrec, J. S., Crozet, C., & d'Ivernois, J. F. (2010). Characteristics and development of therapeutic patient education in rheumatoid. *Joint Bone Spine*, 77, 405-410.

Bandura, A. (1977). *Social learning theory*. Englewood Cliffs, NJ: Prentice Hall.

Bandura, A. (1997). *Self-efficacy: the exercise of control*. New York: Freeman.

Bandura, A. (2004). Swimming against the mainstream: the early years from chilly tributary to transformative mainstream. *Behaviour Research and Therapy*, 42(6), 613-630.

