Official Title: Effects of a Rheumatoid Arthritis Self-management program-a

Randomized Controlled Trial

NCT number: NCT03470740

Date of the document: 20160801

Statistical analysis plan

Data will be double entered for verification and the level of significance is set at alpha of .05 using SPSS Version 22.0. The objective of data analysis is to test the research hypotheses. First of all, descriptive statistical analyses will be used to establish baseline characteristics of rheumatoid arthritis patients using means, ranges, standard deviations, frequencies, and percentages. Background characteristics and outcomes at baseline will be compared between two groups by means of chi-square tests and t-tests for independent samples. To evaluate the effect of the intervention over the total follow-up period, we use the multiple linear regression method used in the Generalized Estimating Equations to take into account of internal dependencies within subjects (due to the repeated measurements) and to adjust for the effects of certain factors.

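### The planned time-by-group test leaves the pre-randomisation baseline as a free outcome; adjusting for baseline would usually give a more precise estimate from data already collected

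*Protocol*

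**What the plan says.** Protocol, Data Analysis, describes a linear GEE: "Effects evaluated included the main effects of time and group and two-way interaction effect(s) of time by group". It says a significant interaction "would indicate a significant change from baseline to a specific later time point between the two groups", and gives the decision rule: "Significant interaction effect(s) in GEE results would provide evidence of intervention effects". The aim is introduced by the words "To evaluate the effect of the intervention over the total follow-up period".

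Protocol, Instruments and Outcome Measurements, gives the schedule: "Outcome data were collected at the baseline, and 2, 3, and 6 months". Sampling Procedure and Procedure and Data Collection both place the baseline measurements before allocation is revealed, and the latter lists a baseline value for every outcome domain.

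The SAP repeats the GEE sentence, including the intention "to adjust for the effects of certain factors", but lists no model terms and no effect contrast. Neither document names the baseline value as a covariate or holds the arms to a common baseline mean.

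**The concern.** Because the interaction is read as change from baseline to a particular later visit, baseline is a level of time and so a row of the outcome. The group main effect then lets the baseline means differ between arms. Under randomisation that difference has expected value zero, so the model estimates something already known, and the noise in that estimate passes into every interaction term.

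What is at stake is precision: confidence intervals that are usually wider, and power that is usually lower, than the trial's own data allow.

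**Working it through.** **Inputs.** From the documents: one baseline and three follow-up visits (2, 3 and 6 months), baseline measured before allocation, and model terms time, group and time-by-group. Not in the documents, so assumed: rho, the SDs, complete data, and categorical time (which the reading of the interaction implies). The only count given is 260 numbered envelopes, used below as an illustrative total with 1:1 allocation. The plan states no precision or power figure, so there is none to reproduce.

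**Step 1: what the planned contrast is.** With categorical time and complete data, each interaction equals the between-arm difference in mean change from baseline to that visit.

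**Step 2: variances at one visit.** Let s0 and s1 be the baseline and follow-up SDs. Per patient:

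- change: s0² + s1² − 2·rho·s0·s1
- baseline-adjusted, slope specific to the visit: s1²(1 − rho²)
- difference (change minus adjusted): (s0 − rho·s1)², which is never negative

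With k = s1/s0, the ratio adjusted/change is k²(1 − rho²)/(1 + k² − 2·rho·k). It equals 1 only at k = 1/rho. With equal SDs it is (1 − rho²)/[2(1 − rho)] = (1 + rho)/2.

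| Assumed rho | Variance ratio | SE falls by |
|---|---|---|
| 0.3 | 0.65 | 19% |
| 0.5 | 0.75 | 13% |
| 0.7 | 0.85 | 8% |
| 0.9 | 0.95 | 2.5% |

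In patient numbers, 260 × 0.75 = 195 at rho 0.5 and 260 × 0.85 = 221 at rho 0.7. So about 196 and 222 patients in two equal arms would match the precision of 260 analysed by change.

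**Step 3: does a baseline main effect help?** No. The covariate has the same value on all four rows of a patient, so it cancels from within-patient change. In one simulated trial (260 patients, rho 0.6, equal SDs, exchangeable working correlation, robust SE) the month-6 SE was 0.1070 for the planned model, 0.1070 with a baseline main effect added, and 0.0927 with centred baseline-by-time also added. The last ratio, 0.0927/0.1070 = 0.87, is close to the large-sample √0.80 = 0.89.

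**Step 4: validity.** In 20,000 simulated trials at each of rho 0.3, 0.6 and 0.9 (true effect 0.30 SD), mean estimates were 0.298 to 0.300 for both methods. Month-6 variance ratios were 0.65, 0.81 and 0.96, against 0.65, 0.80 and 0.95 from the formula.

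**Step 5: an average over follow-up.** With equal SDs and equal correlations, the mean of three visits has variance (1 + 2·rho)/3 per patient. Change gives 4(1 − rho)/3 and adjustment gives (1 − rho)(1 + 3·rho)/3, so the ratio is (1 + 3·rho)/4: 0.475 at rho 0.3, 0.625 at 0.5, 0.775 at 0.7. That is a larger gain than at one visit, but the ordering is not general. Take assumed baseline correlations of 0.70, 0.65 and 0.50 with months 2, 3 and 6, and 0.90, 0.70 and 0.75 for months 2–3, 2–6 and 3–6. The mean then has variance (3 + 2 × 2.35)/9 = 0.856 and covariance 0.617 with baseline. The ratio is (0.856 − 0.380)/(0.856 + 1 − 1.233) = 0.76, so the SE falls 12.6%. At month 6 alone the ratio is 0.75 and the SE falls 13.4%.

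**Step 6: one common baseline slope is not enough.** With rho 0.8 and assumed follow-up SDs of 1, 1 and 1.25 (baseline SD 1), the covariances with baseline are 0.8, 0.8 and 1.0, so the common slope is 0.867. The month-6 variance is then 1.5625 + 0.751 − 1.733 = 0.580, against 0.5625 for change, about 3% worse. The guarantee in Step 2 therefore needs a slope for each visit.

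**The case against.** The strongest reply is that nothing is broken: the model is coherent, its stated interpretation matches its terms, and the test is valid. That stands. A reader might infer bias, an invalid test or a contradiction in the plan; the documents support none of these, because baseline precedes allocation and the change contrast is unbiased.

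Second, the size is unknown. Sample and Setting admits only patients judged stable for at least three months, which may mean a high rho for DAS-28 and MHAQ and so a small gain. It says less about self-efficacy or behaviours. This also stands: it would be too firm to say that the trial will report materially wider intervals.

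Third, a reader might take the averaged figures (SE lower by 31% at rho 0.3) as the loss in this plan. The documents do not support that. The protocol interprets each interaction at a particular visit, and "To evaluate the effect of the intervention over the total follow-up period" can equally describe the span of data in the model. An average of three visits is a contrast the plan does not name, and Step 5 shows that its gain need not be the larger one.

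Fourth, the adjustment promised in "to adjust for the effects of certain factors" might be meant to include baseline. The factors are unnamed, so this cannot be excluded. But as a main effect in the planned model it would change nothing.

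**Conclusion.** The point holds as a free improvement in precision. In large samples, with complete data, the planned contrast is never more precise, and usually less precise, than a same-visit contrast adjusted for baseline with a visit-specific slope. With equal SDs, the standard error would fall by between 2.5% (rho 0.9) and 19% (rho 0.3). The gain vanishes when the follow-up SD divided by the baseline SD equals 1/rho. These figures rest on assumed correlations and SDs and apply to roughly continuous outcomes; the gain for health care utilization, if analysed as a count, may differ.

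**What to change.** Before outcomes are examined by arm, state one of the following for the continuous outcomes in both the protocol's Data Analysis section and the SAP.

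- Keep the GEE with categorical time, group and time-by-group, and add the same outcome's centred baseline value and its interaction with time. The time-by-group terms remain the effect estimates.
- Equivalently with complete data, fit a GEE to the 2-, 3- and 6-month values with baseline, time, group, group-by-time and baseline-by-time, and take the visit-specific group differences as the effect. The rule "Significant interaction effect(s) in GEE results would provide evidence of intervention effects" must then be replaced, because in this model the interaction tests only whether the effect varies between follow-up visits. Patients with no follow-up value contribute no rows here, but they carry little information on the contrast.

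Whether to name an averaged lead contrast is a separate, optional decision.

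The cost is a few lines of text and SPSS syntax, with no new data. Timing is the one constraint, and the documents do not settle it: under the same date, the protocol writes "Data were double entered for verification" and the SAP "Data will be double entered for verification". If outcomes have already been examined by arm, keep the planned contrast and report the adjusted one as a labelled sensitivity analysis.

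### Counting a significant interaction at any of three visits as evidence gives about 12% false positives per outcome if time is categorical; name one baseline-adjusted main test for each outcome

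*Protocol*

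**What the plan says.** The Protocol, under Instruments and Outcome Measurements, states: "Outcome data were collected at the baseline, and 2, 3, and 6 months". It lists six outcomes, ending with "quality of life (SF-36), self-management behaviors, and health care utilization".

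The SAP gives the aim and the model: "To evaluate the effect of the intervention over the total follow-up period, we use the multiple linear regression method used in the Generalized Estimating Equations". Both documents say the model is also meant "to adjust for the effects of certain factors"; the factors are not named.

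Only the Protocol (Data Analysis) says how results will be read. The model has main effects of time and group and their interaction. A significant interaction "would indicate a significant change from baseline to a specific later time point between the two groups", and "Significant interaction effect(s) in GEE results would provide evidence of intervention effects". The SAP does not repeat this rule and puts nothing in its place. Alpha is 0.05 in both documents. Neither names a primary outcome, a primary visit, a joint test or a multiplicity adjustment.

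For utilization, the two documents give no unit, source or recall period. The Protocol says of the data collection, "It followed questionnaire guide to collect data"; that guide is not part of the file.

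**The concern.** The aim is a single effect over all of follow-up, but the reading rule works visit by visit. With baseline as reference and time categorical, each outcome has three interactions, each tested at 5%. If any one of them can support a claim, a program with no effect has three chances per outcome to look effective.

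Each interaction is also a difference in change scores. Subtracting a noisy baseline adds variance that a covariate would not, so real effects are easier to miss.

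Utilization carries one further risk, which depends on how it was recorded. The visits are 2, 1 and 3 months apart. If each report is a raw count since the previous visit, a steady reduction in rate gives three different visit effects and could be read as fading at month 3.

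**Working it through.** The plan gives no sample size, power or overall error rate, so there is no figure of its own to reproduce.

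**Inputs from the documents.** Alpha 0.05; visits at 0, 2, 3 and 6 months; 260 numbered envelopes (Sampling Procedure); "the intervention group received the 6-week RA self-management program".

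**Assumptions.** Two-sided tests; 1:1 allocation, so 260/2 = 130 per arm; complete data. Utilization base case: rate μ = 0.5 events per month, gamma-Poisson counts with between-patient variance φ = 0.5, baseline window b = 3 months, counts since the previous visit (n = 2, 1, 3 months), rate ratio 0.75.

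**1. False positives, general case.** With complete data, the saturated interaction at visit k is the between-group difference in mean Y_k − Y_0. With equal variances and exchangeable correlation ρ:
- Var(Y_k − Y_0) = 2(1 − ρ)σ² and Cov(Y_j − Y_0, Y_k − Y_0) = (1 − ρ)σ², so the three contrasts correlate 0.5 whatever ρ is.
- P(max|Z| > 1.96) = 12.6% for three normal contrasts at correlation 0.5.
- Limit if the contrasts were independent: 1 − 0.95³ = 14.3%.
- First-order autoregressive correlation of 0.3 to 0.95: 10.8% to 12.2%.

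**2. False positives, utilization.** Covariance of changes: μb + φμ²(n_j − b)(n_k − b), plus μn_k on the diagonal. Here μb = 1.5 and φμ² = 0.125.
- Variances: 1.5 + 1.0 + 0.125 = 2.625; 1.5 + 0.5 + 0.5 = 2.5; 1.5 + 1.5 + 0 = 3.0.
- Correlations: 1.75/√(2.625 × 2.5) = 0.68; 1.5/√(2.625 × 3.0) = 0.53; 1.5/√(2.5 × 3.0) = 0.55.
- Simulated any-of-three rate: about 12%. One pooled baseline-adjusted contrast, or a 3-df test, gives 5% to 6%.
- Plain Poisson counts with baseline windows of 1, 2, 3 and 6 months: 13.4%, 12.5%, 11.7%, 10.3%. A gamma-Poisson run of 4,000 trials per window gave 14.8%, 13.4% and 9.1% for 1, 2 and 6 months (Monte Carlo standard error about 0.5 points), so 10% to 14% is a guide and not a strict bound.
- Baseline as covariate but still any-of-three: about 15% (13.7% in a second run). The covariate alone does not repair the error rate.

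**3. Cost of subtracting baseline.** The covariate-adjusted variance is Var(Y_k) − Cov(Y_k, Y_0)²/Var(Y_0), with Var(Y_0) = 1.5 + 0.125 × 9 = 2.625. Control-arm values:
- Month 2: 1.5 − 0.75²/2.625 = 1.29, against 2.625 for the change.
- Month 3: 0.625 − 0.375²/2.625 = 0.57, against 2.5.
- Month 6: 2.625 − 1.125²/2.625 = 2.14, against 3.0.

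Simulated power at the three visits rises from 24/10/44% to 49/30/61% for a constant effect.

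**4. Options compared like for like (base case).**

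| Effect present in | Best single interaction | Best single visit, adjusted | Pooled, adjusted | 3-df, adjusted |
|---|---|---|---|---|
| Months 0–6 | 44% | 61% | 80% | 65% |
| After the 6-week program | 44% | 62% | 54% | 54% |
| Months 3–6 only | 43% | 62% | 27% | 48% |
| Months 0–2 only | 25% | 49% | 15% | 36% |

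The best visit is month 6 in the first three rows and month 2 in the last.

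**5. Unequal windows, if counts run since the previous visit.** Expected effects under a constant reduction: 0.5 × 0.25 × (2, 1, 3) = 0.25, 0.125 and 0.375 events. Under a fixed 3-month recall, the month-2 report holds 2 months after randomisation and 1 before, so dividing by 3 still shows only 2/3 of the effect.

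**6. Across outcomes.** If the six outcomes were independent (an assumption), the chance of at least one false claim is 1 − 0.88⁶ = 54%. Repairing utilization alone leaves 1 − 0.95 × 0.88⁵ = 50%; repairing all six leaves 1 − 0.95⁶ = 26%.

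**The case against.** The strongest reply is that the any-of-three rule is inferred. The Protocol never says one interaction is enough, one of its sentences uses the singular, and a 3-df interaction test would hold about 5%. This stands as a condition on the 12%. It does not remove the point, because no such test is written and the Protocol ties the interaction to individual visits. The 12% also counts both directions: in one run, false claims of reduced use made up 6.2%.

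A reader might infer that change from baseline is biased. It is not, under randomisation; the loss is of precision, and the unnamed covariates do not exclude baseline.

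A reader might infer that utilization was never defined. The documents do not support that, because the questionnaire guide may supply the unit and recall period. The window point is therefore conditional.

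A reader might infer that pooling is simply more powerful. The table shows otherwise: against the best adjusted visit it gains 19 points for a constant effect (80 − 61) but loses 8, 35 and 34 in the other rows. A baseline-adjusted month-6 test is also a valid 5% option, with 61% to 62% power in three of the four timings, though it fails if the effect is confined to months 0–2.

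Finally, the power figures rest on assumed rates and one effect size. At a rate ratio of 0.85, pooled power is 37%; at 0.90 it is 19%.

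**Conclusion.** The concern holds in a limited form. If time is categorical, no joint test comes first and one significant interaction suffices, the false-positive rate is about 12% per outcome instead of 5%. That figure depends little on the utilization assumptions, since it comes from three tests that share a baseline. It applies to every listed outcome, so treating it as a utilization defect alone would leave most of the problem in place.

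The gain from using baseline as a covariate is real but is a matter of efficiency, and its size is illustrative. Which single test has most power depends on when the effect occurs, and the documents do not say. The unequal-window problem arises only for some ways of recording utilization. Overall this is a change that should be made, at low to moderate priority, with medium confidence.

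**What to change.** 1. For each outcome, name one main test of the effect over the whole of follow-up with the baseline value as covariate: either a pooled post-randomisation group contrast or a 3-df joint group test. The pooled contrast suits a sustained effect. The 3-df test gives steadier power across timings (36% to 65% in the base case). Make visit-specific results supportive.
2. Make the two changes together, since the covariate without the single test leaves about 15% false positives.
3. For utilization, state the unit, source and recall period, or point to where the questionnaire guide gives them. If reports are counts since the previous visit, analyse use per month or with an offset of log(months). If recall is a fixed window, use only reports lying wholly after randomisation and state which months they cover. If the window cannot be established, a group comparison of raw counts is still valid, but a per-month contrast over known months is not available.
4. The Protocol describes collection in the past tense. If the data are already in, fix the choice before any unblinded analysis, or report it as not prespecified.

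The cost is SAP wording and, for utilization, one field for months covered, which visit dates or the questionnaire's recall period can supply. The price in power is that of the table: pooling loses when the effect is late or brief. This brings each outcome to about 5%; with six outcomes and no primary, error across outcomes still has to be dealt with separately.
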